This is a multicenter, Phase I trial for children with Retinoblastoma Protein 1 (Rb1) positive recurrent, progressive or refractory central nervous system tumors.

In the recent years there have been several clinical trials in adults with cancer utilizing small molecule inhibitors targeting cell cycle regulatory genes such as CDKs (cyclin-dependent kinase). In normal cells, these kinases are kept under control by a gene, however, this gene is frequently deleted in cancers and these two kinases are uncontrollably activated which drives the cell to divide and form cancer. This trial is using PD-0332991 (palbociclib; IBRANCE), a selective CDK inhibitor, to be evaluated in children with CNS tumors.

PD-0332991 (Pfizer Corporation, USA) is an orally active, water soluble, cell-permeable highly specific inhibitor of CDK4 and 6. It is designed to shut down the activity of molecules, CDK4 and 6 that drive cell division. PD-0332991 is expected to work only if the cancer cells demonstrate expression of the tumor suppressor retinoblastoma (Rb1) protein which is needed to control cell growth even if CDK4/6 is inhibited. A screening test for presence or absence of Rb1 will therefore be performed in all types of CNS tumors except diffuse pontine glioma (DIPG), medulloblastoma, or Atypical Teratoid Rhabdoid Tumor (ATRT) to confirm eligibility for this trial. .

Schema

This is a dose escalation trial of PD-0332991 to determine the maximum tolerated dose in children with recurrent brain tumors. PD-0332991 is taken orally once a day for 21 days followed by a week rest. One course is therefore equivalent to 28 days. Therapy may continue for up to two years (26 courses) in the absence of disease progression or unacceptable toxicity.

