2.3 Rationale

2.3.1 Rationale for version 2.0

Survival for children with recurrent CNS tumors is dismal and novel therapeutic options need to be developed in order to improve outcome. Cancer initiation and progression is dependent on deregulation of the components and phases of the cell cycle. Ample evidence exists (see background section) on alterations of CDKs, Cyclins, cell cycle inhibitors, and checkpoint proteins in pediatric CNS tumors. The presence of specific mutations in the proteins involved in G1-S phase transition of the cell cycle in these tumors is particularly relevant for the use of a specific CDK4/6 inhibitor like PD-0332991. Furthermore, it is likely that over 60% of pediatric CNS tumors are likely to have intact Rb-protein, a pre-requisite for the efficacy of this cell cycle inhibitor. PD-0332991 has not been tested in children with cancer thus far. A Phase I study is therefore needed to assess the toxicity, MTD, pharmacokinetics, and preliminary evidence of efficacy of this agent in this patient population. Since myelosuppression is the predominant side effect of this agent, the Phase I study will first evaluate the toxicities in children who have not been heavily pre-treated previously. Once MTD has been established in this cohort of patients, consideration will be given to expanding the trial to include those who have received intensive cytotoxic therapy including myeloablative chemotherapy +/- craniospinal irradiation. In addition, only patients who have no evidence of cataract formation on ophthalmologic examination will be eligible for this study based on pre-clinical evidence of development of cataracts and lens degeneration in rats treated with PD-0332991 on a 21-day cycle at doses > 30 mg/kg/day for 27 weeks.

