10 STUDY CALENDAR

	Pre-therapy	Course 1	Course 2- Course 26	Completion/ Discontinuation Of Treatment
PHYSICAL ASSESSMENTS				
Medical history	X	Weekly	X	X
Physical exam /height/weight	X	Weekly	X	X
Vital signs	X	Weekly	X	X
Performance status	X	Weekly	X	X
Neurologic exam	X	Weekly	X	X
LABORATORY EVALUATIONS				
CBC - WBC, HgB, Hct, Platelets, ANC, ALC	X	Weekly ^A	Weekly ^{A, B}	X
Serum Chemistry - Sodium, Potassium, Bicarbonate, Chloride, Calcium, BUN, Creatinine, Glucose, Phosphorous, Magnesium, Albumin, Total Protein	X	Weekly	X ^B	X
SGPT (ALT), SGOT (AST), Alkaline phosphatase, Total Bilirubin	X	Weekly	X ^B	X
Serum pregnancy test (for females of childbearing potential)	X	X ^B	X ^B	
CSF cytology (if clinically indicated)	X			
OTHER ASSESSMENT				
12-lead EKG	X	X ^C	X ^C	X ^C
Ophthalmology Examination (including slit lamp)	X		X ^D	
IMAGING ASSESSMENTS				
Brain MRI (standard)	X		X ^E	X
Spine MRI (if clinically indicated)	X		X ^F	X
CORRELATIVE STUDIES				
Screening Pre-trial tumor materials for Rb1 testing (required for patients with all types of CNS tumors except DIPG, medulloblastoma, ATRT)	X ^G			
Pharmacogenetic Studies (if consented)	X ^H			
Plasma Pharmacokinetic Studies (required)	X ^I	X ^I		
Plasma PK after discontinuation of dexamethasone (if consented)		Any time after stopping dexamethasone ^I		
Pre-trial tumor materials for Genomics (if consented)	X ^J			
Tumor Tissue and blood for Biorepository (if consented)	X ^K			

	Pre-therapy	Course 1	Course 2- Course 26	Completion/ Discontinuation Of Treatment

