
A. CBC with differential at baseline and q weekly during each cycle for the first 3 cycles; consideration can be given to increase interval to q 2 weeks from course 4 onwards if the patient has no DLT in the previous cycle. If patient develops Grade 4 neutropenia or thrombocytopenia, then CBCs should be checked every 3-4 days until recovery to Grade 3.
 
B. Within 48 hours of beginning protocol therapy and each course (see 5.3).
 
C. 12-lead EKG at baseline, and 3 hours post dose on days 1, 8, and 15 of cycle 1 and on day 1 of cycles 2 and 3. Thereafter, EKG should be done prior to the start of every 3rd cycle (prior to 6, 9, 12, 15, 18, 21, 24 and end of treatment).
 
D. Eye exam is to be done at baseline, and every 3 months (after courses 3, 6, 9, 12, 15, 18, 21, 24). The ophthalmology exam report should clearly specify the presence or absence of cataracts and data must be recorded in Rave database.
 
E. Standard imaging is to be done every 8 weeks (after courses 2, 4, 6) and then every 12 weeks thereafter through the 26 courses and at the completion of treatment.
 
F. MRI Spine should be done at the same time points as the standard MRI brain, if clinically indicated.
 
G. 2 unstained slides from FFPE block and 1 H&E slide required to be submitted for Rb testing (see 9.1.1)
 
H. Obtain 5 mL of whole blood prior to 1st dose if consented (See section 9.2.1 for details)
 
I. Plasma PK (required) – D1 Course 1: pre-dose, 0.5, 1, 2, 4, 8, 10, 24, 48 hrs after dose D21 Course 1: pre-dose, 1, 2, 4, 8, 10, 24 after dose (See section 9.2.2 for details of Plasma PK) Plasma PK after discontinuation of dexamethasone (if consented) – see section 9.2.2
 
J. 10 unstained slides from FFPE block or FFPE tissue block [See section 9.3.3 for details of Pre-trial tumor materials for Genomics (if consented)]
 
K. Biorepository samples (if consented) – 20 unstained FFPE slides and blood. Obtain 2-5 mL of whole blood at baseline. If unable to collect at baseline, it can be collected any time during protocol therapy. See section 9.3.1 for details.
				

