Hispanic or Latino	5	+	6	= 11
Not Hispanic or Latino	22	+	22	= 44
Ethnic Category: Total of all subjects	27	+	28	= 55
Racial Category				
American Indian or Alaskan Native	0	+	0	= 0
Asian	3	+	3	= 6
Black or African American	6	+	7	= 13
Native Hawaiian or other Pacific Islander	0	+	0	= 0
White	18	+	18	= 36
Racial Category: Total of all subjects	27	+	28	= 55

13.4 Analysis of the Adverse Event Data:

All patients who receive at least 1 dose of protocol therapy will be included in the safety analyses. Adverse event data will be summarized in stratum specific tables which will incorporate dose, attribution as well as grade information.

13.5 Data analysis plan for the secondary objectives:

Any objective responses (PR+CR) which may be observed in this trial will be described by dose and by histology. We will also report prolonged disease stabilizations in a descriptive fashion.

The biology and PD/PG studies are optional in this trial and thus data will be available only from a subset of patients who are likely to represent a variety of histologies. The data generated as part of these correlative studies will be described and summarized in an exploratory fashion via summary statistics and frequency tables as appropriate.

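### A cataract count set against all treated patients includes patients with no scheduled post-baseline eye exam, so a low or zero count can look more reassuring than the data support

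*Combined protocol and SAP*

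**What the plan says.** **Eye exams.** Footnote D of the Study Calendar (section 10) reads "Eye exam is to be done at baseline, and every 3 months (after courses 3, 6, 9, 12, 15, 18, 21, 24". The Schema fixes the course length: "One course is therefore equivalent to 28 days". In the calendar grid the ophthalmology row is marked before therapy and in courses 2 to 26; its completion/discontinuation cell is empty. Footnote D also requires the exam report to say whether cataracts are present and that result to be entered in Rave.

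**Imaging.** Footnote E reads "Standard imaging is to be done every 8 weeks (after courses 2, 4, 6". Under section 5.5.2, progressive disease ends treatment.

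**Safety analysis.** Section 13.4 states "All patients who receive at least 1 dose of protocol therapy will be included in the safety analyses" and "Adverse event data will be summarized in stratum specific tables which will incorporate dose, attribution as well as grade information". It defines no group evaluable for eye findings, and no cataract rate, interval or precision target.

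**Why the eye is watched.** Section 2.3.1 says "only patients who have no evidence of cataract formation on ophthalmologic examination will be eligible for this study", on the strength of the rat findings, and section 3.3.8 makes baseline cataract an exclusion. Describing toxicity is part of primary objective 1.1.1.

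**The concern.** Neutropenia or vomiting can show itself at any visit. An early cataract is found mainly because someone looks with a slit lamp, so the patients who inform the cataract question are those who were looked at. The all-treated safety population also contains patients who left before the first scheduled look.

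The design makes such departures likely. The first on-treatment MRI comes one course before the first on-treatment eye exam, so a patient who progresses on that scan leaves first. In section 6.2, a dose-limiting toxicity at dose level 1, where stratum II starts, also ends treatment.

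The routine adverse event table may not settle the matter. Section 7 records grade 1 and 2 events only if they are at least possibly related to the drug, and section 7.1 lists cataract among events with insufficient evidence of causation. A mild cataract judged unrelated could be in the eye-exam data and absent from the adverse event table.

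At stake is how a statement such as no cataracts in 21 patients would be read, for a toxicity that the protocol took seriously enough to write into eligibility.

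**Working it through.** **Plan's own figures.** The documents give no cataract rate or interval to reproduce. The denominators do reproduce: six patients per dose level plus a six-patient expansion gives 6 × 3 + 6 = 24 for stratum I and 6 × 2 + 6 = 18 for stratum II, as section 13.3 states. Stratum I closed with 3 + 12 + 6 = 21 enrolled (Schema). I take all 21 as treated, and 18 as the stratum II maximum.

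**Timing.**
- First on-treatment MRI: 2 × 28 = 56 days, week 8.
- First on-treatment eye exam: 3 × 28 = 84 days, week 12.
- A patient who stops between later exams likewise has no scheduled exam covering the last interval.

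**Effect on an upper bound.** The share *s* stopping before the end of course 3 is an assumption, taken as 20%, 40% or 60%. The number examined is *m* = *N*(1 − *s*), rounded. With zero events, the one-sided 95% upper bound is 1 − 0.05^(1/*m*).

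| | All treated | *s* = 20% | *s* = 40% | *s* = 60% |
|---|---|---|---|---|
| Stratum I, number | 21 | 17 | 13 | 8 |
| Zero cataracts, upper bound | 13.3% | 16.2% | 20.6% | 31.2% |
| One cataract, percentage | 4.8% | 5.9% | 7.7% | 12.5% |
| Stratum II, number | 18 | 14 | 11 | 7 |
| Zero cataracts, upper bound | 15.3% | 19.3% | 23.8% | 34.8% |

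For example, 1 − 0.05^(1/21) = 0.133 and 1 − 0.05^(1/13) = 0.206. With zero cataracts the point estimate is 0 under either denominator; only the bound moves.

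**Is the all-treated rate biased?** Let the risk be *p* in examined patients and *q* in unexamined patients. The observed all-treated rate is *p*(1 − *s*); the true one is *p*(1 − *s*) + *qs*. With *p* = 10% and *s* = 40%, the observed rate is 0.10 × 0.60 = 6.0%. The true rate is:
- *q* = 0: 6.0%, so no bias;
- *q* = 5%: 6.0% + 2.0% = 8.0%;
- *q* = 10%: 6.0% + 4.0% = 10.0%.

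The direction and size of any bias therefore rest on *q*, which a schedule without early or exit exams cannot show.

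**What the animal data say about *q*.** Section 2.2.2.1 reports cataracts in rats after 27 weeks of three-weeks-on, one-week-off dosing, and no drug-related ocular toxicity in the 15-week rat and dog studies. Twenty-seven weeks is 27/4 = 6.75 courses. Without claiming that rat and human timing match, the first scheduled exam beyond that duration is the one after course 9, at 36 weeks.

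**The case against.** The strongest objection is that the plan produces nothing that could be wrong. Section 13.4 offers descriptive tables by stratum, without a cataract percentage or interval, and does not say that an unexamined patient is classed as free of cataract. That stands. The problem arises only when someone reads or reports the count against all treated patients, which the absence of any other denominator invites.

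A reader might infer that the cataract rate is bound to be understated. The documents do not support that. The animal timing makes a low risk before week 12 plausible, and with no cataracts in early stoppers the all-treated rate is unbiased. The same timing, however, argues for reporting by exposure: if the toxicity is late, patients with one or two courses say little about it. Restricting to examined patients also conditions on staying on treatment to about week 12. That is a different quantity, not an automatic correction, so both numbers should be shown.

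A reader might also infer that early stoppers are never examined again. The calendar shows only that no exam is scheduled. A symptom-driven exam remains possible, and section 5.5.3 follows related toxicities occurring up to 30 days after the last dose.

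The empty discontinuation cell might be taken for an inconsistency, because the EKG schedule in footnote C runs "prior to 6, 9, 12, 15, 18, 21, 24 and end of treatment". Different assessments may have different schedules, and the pregnancy-test row has an empty completion cell too. This is not a contradiction, and an exit exam would be an added procedure.

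Finally, no dose decision depends on the point. Only toxicities in the dose-finding period guide escalation (sections 5.1.1 and 5.2), so a cataract first seen at week 12 cannot change the MTD. That stands and limits the weight of the point.

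**Conclusion.** The point holds as a cheap improvement to reporting. The exam schedule and the all-treated safety population are as described, and together they allow a low or zero cataract count to look more reassuring than the number of examined eyes supports. In stratum I the zero-event bound would move from 13.3% to between 16.2% and 31.2%, and in stratum II from 15.3% to between 19.3% and 34.8%. These ranges rest on an assumed early-stop share of 20% to 60%, on all 21 stratum I patients having been dosed, on stratum II reaching 18, on every patient who completes course 3 being examined, and on no unscheduled exams. They illustrate how a reader might interpret a count; the plan specifies no such bound. Bias in the all-treated rate is possible but not established.

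**What to change.** Add one sentence to section 13.4: cataract findings, and other lens findings where recorded, will be reported by stratum among patients with at least one post-baseline slit-lamp exam, by number of courses received at the last exam, together with the number of treated patients who had no post-baseline exam. Keep the all-treated adverse event tables as they are.

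The cost is that sentence and one table. Cataract presence or absence is already required in Rave, so the change needs no new procedure and can cover stratum I, although that stratum is closed. The downside is a smaller denominator and less favourable apparent precision. The table should also say that it describes patients who stayed on study long enough to be examined.

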11 MEASUREMENT OF EFFECT

11.1 Tumor Response Criteria

11.1.1 Complete Response (CR)

Complete disappearance on MR of all enhancing tumor and mass effect, on a stable or decreasing dose of corticosteroids (or receiving only adrenal replacement doses), accompanied by a stable or improving neurologic examination, and maintained for at least 8 weeks. If CSF was positive for malignant cells, it must be negative.

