3.2.2 Measureable Disease

Patients must have measurable disease (in 2-dimensions) on MRI scan of brain and/or spine to assess preliminary evidence of response.

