11.1.2 Partial Response (PR)

Greater than or equal to 50% reduction in tumor size by bi-dimensional measurement, as compared with the baseline measurements, on a stable or decreasing dose of corticosteroids, accompanied by a stable or improving neurologic examination, and maintained for at least 8 weeks. If CSF was positive for malignant cells, it must be negative.

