11.1.3 Stable Disease (SD)

Neurologic exam is at least stable and maintenance corticosteroid dose not increased, and MR/CT imaging meets neither the criteria for PR nor PD. CSF can be positive or negative for malignant cells. If this category is to be reported as of possible clinical benefit, Stable Disease status must be maintained for at least 4 courses.

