11.1.4 Progressive Disease (PD)

Progressive Disease (PD): Progressive neurologic abnormalities or worsening neurologic status not explained by causes unrelated to tumor progression (e.g., anticonvulsant or corticosteroid toxicity, electrolyte disturbances, sepsis, hyperglycemia, etc.), OR a greater than 25% increase in the bi-dimensional measurement, taking as a reference the smallest disease measurement recorded since the start of protocol therapy, OR the appearance of a new lesion (including new appearance of malignant cells in the CSF), OR increasing doses of corticosteroids required to maintain stable neurological status or imaging.

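### The CR imaging test covers only enhancing tumor and mass effect, so a residual non-enhancing tumor that falls short of PR can fit the wording of both CR and SD

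*Combined protocol and SAP*

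**What the plan says.** The response categories in section 11.1 do not all refer to the same tumor.

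- **CR (11.1.1):** the imaging test is "Complete disappearance on MR of all enhancing tumor and mass effect". The remaining conditions are a steroid dose that is not rising (adrenal replacement is allowed), a response "accompanied by a stable or improving neurologic examination, and maintained for at least 8 weeks", and CSF that has cleared if it was positive.
- **PR (11.1.2):** "Greater than or equal to 50% reduction in tumor size by bi-dimensional measurement, as compared with the baseline measurements". The steroid, neurologic, eight-week and CSF conditions are essentially those of CR.
- **SD (11.1.3):** on imaging, "MR/CT imaging meets neither the criteria for PR nor PD". CR is not named among the exclusions.
- **PD (11.1.4):** among other triggers, "a greater than 25% increase in the bi-dimensional measurement" over the smallest measurement since the start of therapy.
- **Entry (3.2.2):** "Patients must have measurable disease (in 2-dimensions) on MRI scan of brain and/or spine to assess preliminary evidence of response".

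Enhancement appears in the CR definition alone. Section 13.1.2 makes every eligible patient who took at least one dose evaluable for response. Section 13.5 will describe PR and CR by dose and by histology. Section 9.4.2 sends the scans of documented responders to central review at study completion.

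**The concern.** Response categories should be ordered and mutually exclusive: a CR should also clear the PR threshold, and a scan should have one category. The SD wording relies on this. If all measured tumor has gone, the reduction is 100%, the PR imaging threshold is passed, and excluding PR from SD also excludes CR. Limiting CR to enhancing tumor breaks that nesting, because non-enhancing tumor that was part of the baseline measurement may remain.

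The stake is how individual responses are reported. Section 13.6 expects objective responses to be rare, and a listing by dose and histology has small cells, so one patient moved from SD to CR would stand out. The duration requirement changes too. SD must last at least four courses (4 × 28 days = 16 weeks) before it may be reported as possible clinical benefit; CR needs eight weeks.

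**Working it through.** The plan states no figure to reproduce. The check applies the definitions, as worded, to illustrative measurements; the sizes are assumptions.

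**Case 1.** The baseline tumor is mostly non-enhancing with an enhancing nodule. At follow-up, enhancement and mass effect are gone and non-enhancing tumor remains. Steroid, neurologic, eight-week and CSF conditions are met.

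- Baseline product: 40 × 35 = 1400 mm².
- Residual product: 34 × 31 = 1054 mm².
- Change: 1054/1400 − 1 = −24.7%.
- PR limit: 0.50 × 1400 = 700 mm² or less.

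| Category | Test applied to case 1 | Met? |
|---|---|---|
| CR | no enhancing tumor, no mass effect | yes |
| PR | 1054 ≤ 700 mm² | no |
| PD | increase above 25%, or another trigger | no |
| SD | neither PR nor PD; neurology at least stable; steroids not increased | yes |

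The patient fits CR and SD and does not fit PR.

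**Case 2: does this need a large residual?** Baseline 15 × 12 = 180 mm²; non-enhancing residual 13 × 11 = 143 mm²; change 143/180 − 1 = −20.6%; PR needs 90 mm² or less. The result is the same, so the conflict does not depend on a bulky residual without mass effect.

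**Boundaries.** If the case 1 residual were 700 mm² or less, the scan would meet both CR and PR. The PR+CR total would then be unaffected and only the split would change. If the tumor enhances throughout and disappears, CR is scored as intended. The total is at risk only when a non-enhancing residual exceeds half the baseline product.

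**Does another section close the gap?** I found none that does. Section 3.2.2 does not limit measurable disease to enhancing lesions, 13.1.2 does not exclude non-enhancing disease, 9.4.1 and 9.4.2 give no separate response definition for central review, and 13.5 sets no precedence between categories.

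**The case against.** The strongest reply is that the text does not force CR. Case 1 fits SD word for word, and a sensible reader would choose SD. That stands as far as it goes: the defect is an overlap without a precedence rule. But the SD reading does not cancel the CR reading, and two sites could score the same scan differently.

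Mass effect must also resolve completely, along with the steroid, neurologic, eight-week and CSF conditions. This also stands. A reader might infer that any patient with non-enhancing disease could be turned from SD to CR; the documents support that only when all these conditions hold and the residual still exceeds half of baseline.

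A reader might also infer that a wholly non-enhancing tumor meets the enhancing-tumor part of CR from baseline. That treats the test as met when there was nothing to disappear. Disappearance can fairly be read as requiring enhancement at the outset, so I do not rely on this case.

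It is tempting to convert the gap into a number of affected patients or a shift in response rate. The documents do not give the share of patients with non-enhancing measurable disease. The planning maxima of 24 and 18 are dose-finding figures, Stratum I has closed with 21 enrolled, and no overall response rate is planned.

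Finally, central review compares baseline, response and confirmation scans and discusses disagreements with the site. A reviewer may well question a visible residual, so this is a partial safeguard. It would be too strong to say that review cannot catch such a case; but the protocol gives the reviewer no different definition on which to overrule it.

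**Conclusion.** The CR definition is wrong as written: its imaging test covers less tumor than entry, PR and PD do, and SD does not exclude it. In the worked case a 24.7% reduction, about half the 50% needed for PR, fits the wording of CR and of SD. This follows from the text; only the measurements are assumed.

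The consequence is limited. Frequency cannot be estimated from the documents. What is exposed is the descriptive PR+CR listing, which serves a secondary objective (1.2.1) and carries no test or decision threshold. DLT assessment, escalation, the MTD and the sample size do not depend on it, and continuing treatment requires only at least stable disease (5.3), which either category satisfies. It is still worth correcting, because each reported response will be read individually.

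**What to change.** 1. In 11.1.1, insert *and non-enhancing* after the word enhancing, and *identified at baseline* after the word tumor. Leave the mass-effect, steroid, neurologic, eight-week and CSF conditions unchanged.
2. In 11.1.3, state that imaging meets *none of the criteria for CR, PR or PD*.
3. In 9.4.2, state that the end-of-study central review applies these definitions to all reported responses in both strata.

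Limiting measurable disease, PR and PD to enhancing tumor would also align the categories, but it would change three definitions and the meaning of an entry criterion after Stratum I has completed enrollment.

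No new brain scan is needed, since 9.4 already requires brain MRI with and without contrast. The cost is that the CR count can only fall, with some cases moving to PR or SD, and that any CR already recorded in Stratum I must be re-read against the new wording. Accrual to Stratum II was ongoing at this version and central review takes place at study completion, so the corrected definition can still govern what is reported.
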